## 6.4 Treatment compliance

Designated site personnel will ensure treatment compliance by overseeing SC infusion of the IMP by the participant. Drug accountability must be recorded on the Drug Accountability form. Any incomplete administration of IMP will require documentation of how much was infused (including start and stop times).

## 6.5 Concomitant medication(s)/treatment(s)

### 6.5.1 Permitted concomitant treatments (medications and therapies)

The following concomitant medications are permitted during the study:

- With approval from the investigator, paracetamol is permitted for the treatment of mild symptoms (eg, headache or pain), given at most [REDACTED], not exceeding 2g/day, and with a total of no more than 10g per [REDACTED].
- Hormonal contraceptives, implants, patches, intrauterine hormone-releasing system, or intrauterine devices delivering progesterone or postmenopausal hormonal replacement therapy (HRT) are allowed in female participants.

### 6.5.2 Prohibited concomitant treatments (medications and therapies)

With the exception of vitamins and the permitted concomitant treatments noted in Section 6.5.1, all prescription medication (including herbal medications) or over-the-counter medicines are prohibited from 14 days prior to dosing until follow-up (Day 57), unless required to treat an AE, including pretreatment. Vaccinations are not allowed during the study.

### 6.5.3 Rescue medication

In the case of prolonged hypogammaglobulinemia, the study participant will be considered for treatment with prophylactic antimicrobial therapy and, where appropriate, a commercially available intravenous immunoglobulin. Study participants will be followed up until immunoglobulin levels return to within the normal range. The date and time of rescue medication administration as well as the name and dosage regimen of the rescue medication must be recorded.

## 6.6 Dose modification

No dose modifications are allowed during the study for an individual study participant.

## 6.7 Criteria for study hold or dosing stoppage

A rapid response procedure (Rapid Alert) for communicating serious and/or severe AEs or any other safety findings as described below will be operational during the study. A description of Rapid Alert procedures and how they may be used to facilitate prompt decision making regarding stopping exposure to study medication/procedures is provided in Appendix 8 (Section 10.8). The Rapid Alert Process should occur for any SAE or any severe AEs, regardless of relatedness to IMP that occurs during the study period. Detailed procedures for reporting SAEs and other safety events that may meet study hold criteria are provided in Appendix 3 (Section 10.3) and Appendix 8 (Section 10.8).

### 6.7.1 Stopping rules for all cohorts

If any of the following stopping criteria are met in any of the study cohorts, further dosing will be placed on hold:

- One study participant in the cohort has an SAE considered related to the IMP as judged by the investigator.
- One study participant in the cohort has anaphylaxis considered related to the IMP as judged by the investigator (Appendix 12 [Section 10.12]).
- More than one study participant within the same cohort has a severe nonserious AE considered related to the IMP as judged by the investigator.

If any of the stopping criteria has been met, further dosing will be suspended in all cohorts until further information is collected to assess the relationship with IMP. If additional information shows there is no relationship with IMP (eg, study participant was on placebo after unblinding), dosing can continue as planned. If it is deemed appropriate to restart dosing, a request to restart dosing with pertinent data will then be submitted as a request for a substantial amendment.

All safety and tolerability data (including serious and nonserious AEs) will be reviewed on a rolling basis by the investigator and sponsor's Study and Safety Physician (or designee). Safety evaluation of all available information across all cohorts will be completed by the SMC, including all serious AEs considered related to the IMP. In case of a safety signal, the SMC can recommend at any time to hold further dosing in a cohort. Restart of dosing within a cohort can be decided by the SMC if, after proper investigation, the safety signal is deemed to be not clinically relevant and when the below stopping criteria are not met.

Following case review to confirm causality and seriousness and/or severity of reported events, UCB will halt further dosing if during the study there is an SAE or 2 severe or clinically significant AEs considered to be at least possibly related to the IMP. A severe AE is defined as a Common Terminology Criteria for Adverse Events grade  $\geq 3$ . If following an internal safety review, it is appropriate to restart the study, a substantial amendment will be submitted to the regulatory authority and independent ethics committee (IEC). The study will not restart until the amendment has been approved by the regulatory authority and IEC.

If no further dosing is planned due to the stopping criteria described above, previously randomized and dosed study participants will continue the study as planned. Safety assessments will be performed per the protocol. Pharmacokinetic and PD assessments will be performed if deemed to be relevant and agreed by the investigator and sponsor without compromising the safety of a study participant.

Other reasons for stopping and terminating the study will be:

- A pattern of AEs occurs that, in the opinion of the investigator and/or SMC, contraindicates further dosing of enrolled/additional study participants.
- If the sponsor or its designee judges it necessary for medical, safety, regulatory, or any other reasons consistent with applicable laws, regulations, and Good Clinical Practice (GCP).
- The sponsor decides to terminate the study, and no further dosing will be scheduled.

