## 4 STUDY DESIGN

### 4.1 Overall design

This Phase 1 study is a randomized, participant-blind, investigator-blind, placebo-controlled safety/tolerability, PK, and PD evaluation of a [REDACTED] rozanolixizumab SC dose administered to healthy participants by either a programmed syringe driver or by MP via self-administration. As rozanolixizumab has not been administered SC to humans by MP, this study represents a preliminary assessment of the MP method prior to recommendation of this administration technique in the clinical dosing of rozanolixizumab.

Participants will be divided into 2 body weight categories:  $\geq 35$  to  $< 50$ kg and  $\geq 50$ kg. Within the higher body weight category, 16 participants will be randomly allocated to syringe driver or MP cohorts and, subsequently, to rozanolixizumab (6 participants total) or placebo (2 participants total) (Figure 1-1). Participants of lighter body weights between  $\geq 35$  to  $< 50$ kg are being investigated to a) support the newly recommended rozanolixizumab dosing with a fixed dose of [REDACTED] in adults of  $\geq 35$ kg to 50kg (via syringe driver administration) and (b) to assess the MP method for a [REDACTED] IMP volume.

Within the lower body weight category, the allocation to either syringe driver or MP will be determined by order of recruitment rather than randomization. The first 8 participants will be allocated to the syringe driver cohort and randomly allocated to receive either rozanolixizumab [REDACTED] (6 participants total) or placebo (2 participants total). The subsequent 8 participants will be allocated to the MP cohort and randomly allocated to receive either rozanolixizumab [REDACTED] (6 participants total) or placebo (2 participants total).

The treatment groups are planned to be as follows:

- Cohort 1 (participants with a body weight of  $\geq 35$ kg to  $< 50$ kg) is planned to have 6 participants receive rozanolixizumab [REDACTED] and 2 participants receive placebo via syringe driver at a [REDACTED].
- Cohort 2 (participants with a body weight of  $\geq 35$ kg to  $< 50$ kg) is planned to have 6 participants receive rozanolixizumab [REDACTED] and 2 participants receive placebo via MP through self-administration at a [REDACTED].
- Cohort 3 (participants with a body weight of  $\geq 50$ kg) is planned to have 6 participants receive rozanolixizumab [REDACTED] and 2 participants receive placebo via syringe driver at a [REDACTED].

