- Cohort 4 (participants with a body weight of  $\geq 50$ kg) is planned to have 6 participants receive rozanolixizumab [REDACTED] and 2 participants receive placebo via MP through self-administration at a [REDACTED].

Since a [REDACTED] rozanolixizumab fixed dose has not been investigated thus far in lower weight (35 to 50kg) healthy participants, 2 sentinel study participants (1 active + 1 placebo) will be incorporated into Cohort 1 in order to collect safety and tolerability data over a 72-hour period. The SMC will convene to evaluate all available safety and tolerability data following completion of a 72-hour evaluation period and prior to staggered dosing of remaining participants in Cohort 1. As a further precautionary step for Cohort 1, dosing of the 6 post-sentinel participants will be staggered such that no more than 2 participants will be dosed in a 72-hour period with a

minimum of 48 hours between participants. In addition, the Rapid Alert process is in place throughout the study to ensure that exposure to the study medication is stopped if a reported event meets the stopping criteria (see Appendix 8 [Section 10.8]). Cohorts are not obliged to run in numerical sequence (ie, cohorts could run in parallel).

Since MP IMP administrations in this study will likely be at higher infusion rates than the [REDACTED] SC rate undertaken in all rozanolixizumab clinical studies to date, 2 sentinel study participants (1 active + 1 placebo) will be incorporated into Cohorts 2 and 4. Review of 48-hour postdose safety data by the SMC will enable dosing of the remaining participants (see Section 9.7 and Appendix 8 [Section 10.8]).

The eligibility of study participants will be determined during a Screening Period of up to 4 weeks (Day -28 to Day -2). Once eligibility is confirmed, the study participant will be admitted to the site (at Day -1 or the evening of Day -2) and will enter an In-Clinic Period through Day 5. Each study participant will receive a [REDACTED] SC dose of rozanolixizumab on Day 1 and may be discharged beginning at Day 5 at the discretion of the investigator. Each participant will only receive [REDACTED] IMP administration.

Beginning at Day 6, study participants will enter the Ambulatory Period and will attend the clinical site for study visits through Day 57 to allow sufficient time for systemic IgG levels to return to Baseline and for the assessment of anti-drug antibodies (ADAs).

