**Table 6-1: Study treatments**

Study Treatment Name:	Rozanolixizumab		Placebo	
	Syringe Driver	Manual Push	Syringe Driver	Manual Push
Dosage formulation:	Solution for injection		Solution for injection	
Unit dose strength:	██████████		Not applicable	
Dose level	██████████ (MP or Syringe Driver)		Not applicable	
Volume	██████████ ██████████		██████████ ██████████	
Route of Administration	Subcutaneous infusion		Subcutaneous infusion	
Use	Investigational		Placebo	
Infusion site:	Abdomen		Abdomen	
Infusion rate:	██████████ ██████████	Unspecified (individually variable)	██████████ ██████████	Unspecified (individually variable)
Expected Duration of infusion:	██████████	Unspecified (individually variable)	██████████	Unspecified (individually variable)

MP=manual push

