## 10.8 Appendix 8: Rapid alert procedures

The aim of the Rapid Alert process is to stop the exposure to the study medication or concerned study procedure as soon as possible, following a confirmed or suspected safety issue, preventing its reoccurrence in other study participants. Upon occurrence of an SAE and/or another safety event including stopping rules for all cohorts which may constitute a study hold criteria, irrespective of its relationship with the study medication or the study conduct, the **investigator must notify the study sponsor as soon as possible** (ideally within 2 hours of becoming aware of the event) by the following process:

1. A phone call to the Study Physician to alert them a safety event has been identified.
2. If the investigator is not able to reach the Study Physician, they should call the 24h rapid response helpline number. Upon receipt of a call from an investigator, the 24/7 helpline will contact a physician from UCB who will return the call to the investigator.
3. Additionally, send a completed “Investigator (S)AE Report Form for Development Drug (For Rapid Alert Studies)” to the fax/email for Rapid Alert provided at the front of the protocol. The form should include assessed seriousness, severity, and causality and should be filed in the Study Investigator’s File.

Both the phone call and the completed form from the investigator are crucial in assessing the safety of the study medication and in determining whether the event requires immediate action to place the study on hold and/or expedite reporting to the regulatory authorities. The (S)AE form should be completed in English and provided even if the data are incomplete, or if it is obvious that more data will be needed in order to draw any conclusions about the diagnosis or causality. Additional information (eg, laboratory reports) received by the investigator must be provided within 24 hours. All documents in the local language must be accompanied by a translation in English, or the relevant information included in the same document must be summarized in English in the (S)AE form.

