During the call between the investigator and the UCB physician the safety issue will be discussed to determine if there is sufficient evidence to declare a protocol hold criteria has been met. If the investigator and UCB physician agree a stopping a criterion has not been met, dosing of the study may continue as per the study protocol and the discussion between the investigator and the UCB physician should be documented. UCB will not downgrade the investigator decision to halt the study if the investigator considered that a stopping criterion has been fulfilled.

In all other circumstances, the investigator will be instructed to suspend dosing and the UCB physician will arrange an urgent, internal UCB Rapid Alert Team meeting. The Rapid Alert Team will review the information provided at the call along with the (S)AE form to determine whether or not a protocol hold criterion has been met. If it is determined the criterion has not been met, UCB will contact the investigator and inform them to recommence dosing. If it is determined a hold criterion has been met, UCB will contact all investigators and notify them of the formal hold.

If the investigator believes a protocol stopping criterion has been met, and they are unable to contact UCB prior to the next dose being due, they should postpone any further dosing until they

---

have obtained feedback from UCB. In these circumstances dosing may be restarted if UCB and the investigator subsequently agree that no stopping criteria have been met.

PUBLIC COPY  
This document cannot be used to support any marketing authorization application and any extensions or variations thereof.

---

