5.3.2 Main analytical approach

All AEs and serious adverse events (SAEs) will be collected from the signing of the ICF until the Safety Follow-up/Withdrawal Visit. All AEs will be coded ([Section 5.1.1.5](#)) and categorized by intensity (mild/moderate/severe) and relationship to study drug (related/not related). Only TEAEs will be included in the summary tables and listings.

The number and percentage of participants who experience TEAEs will be summarized by cohort, treatment group, system organ class (SOC) and preferred term (PT) based on the safety analysis set. Summaries of TEAEs will include the following:

- Overview of TEAEs (overview including number and percentage of participants with any TEAEs, serious TEAEs, discontinuations due to TEAEs, drug-related TEAEs, severe TEAEs, TEAEs of special interest and TEAEs leading to death; event counts will also be included)
- Incidence of TEAEs
- Incidence of TEAEs leading to study medication interruption
- Incidence of serious TEAEs
- Incidence of non-serious TEAEs
- Incidence of TEAEs by relationship to study medication
- Incidence of TEAEs by maximum relationship to study medication
- Incidence of TEAEs by intensity
- Incidence of TEAEs by maximum intensity
- Incidence of non-serious TEAEs by relationship
- Incidence of serious TEAEs by relationship
- Incidence TEAEs of special interest
- Incidence of TEAEs of Focus (see Appendix 6.1.8)
- Incidence of TEAEs of special monitoring
- Incidence of TEAEs by TE ADA status

In case of missing or incomplete dates, AEs will be assumed to be treatment-emergent and will be handled as described in [Section 6.1.5.3](#).

Summary tables will contain counts of participants, percentages of participants (in parentheses), and the number of events where applicable. A participant who has multiple events in the same SOC and PT will be counted only once in the participant counts but all events will be included.

In summaries including relationship, the following relationships will be summarized: 'not related', 'related'. Participants who experience the same event multiple times will be included in the most related category for tabulations by maximum relationship. Events with missing relationship will be considered as 'related' but recorded as missing in the listings.

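### Section 6.7.1 lets placebo status clear a dosing hold, although placebo in Cohorts 2 and 4 is given by the manual push under test

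*Protocol*

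**What the plan says.** Protocol Section 6.7.1 has three criteria, each tied to the investigator's judgement that the event is related to the IMP: one SAE, one case of anaphylaxis, or, for severe nonserious events, "More than one study participant within the same cohort has a severe nonserious AE considered related to the IMP as judged by the investigator". Meeting any of them suspends dosing in all cohorts. The way out is this sentence: "If additional information shows there is no relationship with IMP (eg, study participant was on placebo after unblinding), dosing can continue as planned". The same section adds a sponsor halt across the whole study for an SAE, or for two severe or clinically significant AEs, at least possibly related to the IMP.

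Section 4.1 plans 6 active and 2 placebo participants in each cohort. For Cohorts 2 and 4 the placebo arm reads "and 2 participants receive placebo via MP through self-administration". The sentinel pair in each of these cohorts (1 active, 1 placebo) is justified by the speed of the push: "Since MP IMP administrations in this study will likely be at higher infusion rates than the" rate used in earlier studies (figure redacted). Table 6-1 leaves the manual-push rate unspecified. The primary objective is safety and tolerability by manual push versus syringe driver.

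Appendix 8 (Section 10.8) opens broadly: "The aim of the Rapid Alert process is to stop the exposure to the study medication or concerned study procedure as soon as possible". Its decision step is narrower. The investigator and the sponsor's physician talk to "determine if there is sufficient evidence to declare a protocol hold criteria has been met".

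**The concern.** Unblinding to placebo rules out rozanolixizumab as the cause. It does not rule out the push, or the volume or solution that was pushed. In this trial the push is part of what is being tested for safety, so a severe site reaction after placebo by manual push is evidence about the method. The 6.7.1 example nevertheless treats it as a reason to go on.

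Suppose two Cohort 4 participants have severe injection-site reactions, both rated IMP-related under blind, and dosing is held. One turns out to be on placebo. If that case is set aside, one remains, the criterion is no longer met, and manual push can continue without the substantial amendment that a restart would otherwise need. Yet the placebo case was the clearest pointer to the push.

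At stake is the protection of healthy volunteers during dosing. Reporting is not affected: SAP Section 5.1.1.3 keeps placebo-by-manual-push groups, so these events still appear in the safety tables.

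**Working it through.** **Headcount.** 4 cohorts × (6 + 2) = 32 participants, 24 on rozanolixizumab, as the protocol states. Manual push: 2 × 8 = 16 participants, of whom 4 are on placebo. The documents give no operating characteristics for the stopping rules.

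**Does any numeric rule count a method-caused event on placebo?**
- The three per-cohort criteria: no, each requires relationship to the IMP.
- The sponsor's study-wide halt: no, same requirement.
- Rapid Alert: triggered by any SAE or severe AE regardless of relatedness (Section 6.7), but its decision returns to the hold criteria, none of which concerns a procedure.
- Causality assessment: Appendix 3 asks about study medication, and SAP Section 5.3.2 classes events as related or not related to study drug. Appendix 7 on device events is marked not applicable.

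**One-participant criteria.** If a method-caused event is equally likely in every manual-push participant, it falls on placebo with chance 4/16 = 25%, or 1/2 = 50% within a sentinel pair. The study-wide rule does not change this, because it too needs an IMP-related SAE.

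**Severe nonserious criterion.** Assumptions, none of them from the documents: risk q per active and r per placebo participant in both manual-push cohorts; participants independent; no qualifying syringe-driver events; every placebo event is set aside.

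A hold in one cohort needs at least 2 of its 8 participants affected. With r = q:

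P(hold) = 1 − (1−q)^8 − 8q(1−q)^7

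At q = 0.10: 1 − 0.4305 − 0.3826 = 0.1869.

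The hold is clearable only if fewer than 2 active participants are affected across both manual-push cohorts by study end; otherwise the study-wide rule still bites. The qualifying patterns (active in cohort, placebo in cohort, active in the other cohort) are (1,1,0), (0,2,0), (0,2,1) and (1,2,0). Their sum is

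P(clearable) = 12·q·r(1−r)(1−q)^11 + r²[(1−q)^12 + 12q(1−q)^11]

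With r = q = 0.10: 0.0339 + 0.0028 + 0.0019 + 0.0019 = 0.0405, and 0.0405/0.1869 = 22%.

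| q (r = q) | P(hold) | P(clearable) | Share of holds |
|---|---|---|---|
| 2% | 0.0103 | 0.0042 | 40% |
| 5% | 0.0572 | 0.0184 | 32% |
| 10% | 0.1869 | 0.0405 | 22% |
| 20% | 0.4967 | 0.0440 | 9% |

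**Sensitivity.** The placebo's composition is not given, so its risk may be lower. With r = q/2,

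P(hold) = 1 − (1−q)^6(1−r)^2 − 6q(1−q)^5(1−r)^2 − 2r(1−r)(1−q)^6

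This gives 0.0079, 0.0447, 0.1501 and 0.4220. The clearable probabilities are 0.0020, 0.0089, 0.0195 and 0.0213, so the shares are 25%, 20%, 13% and 5%.

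**The case against.** The strongest reply is that mandatory review surrounds this sentence. Every SAE or severe AE goes through Rapid Alert whatever its cause. Dosing continues only if the investigator and the sponsor's physician agree that no criterion is met, and the sponsor will not downgrade an investigator's decision to halt. SMC review of 48-hour sentinel data is required before the rest of Cohorts 2 and 4 are dosed. The SMC may hold a cohort for a safety signal, and a pattern of AEs can stop dosing with no relatedness condition. The study-wide rule keeps a remaining active case in play: one more qualifying event in any cohort halts dosing. Injection site reactions in UP0060 were all mild, and the SMC Charter, which was not available, may already cover the point.

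Most of this stands, and it rules out three stronger readings that a reader might infer:
- That a placebo event forces a restart. The sentence says dosing can continue, and placebo is only an example.
- That no other predefined route exists. Rapid Alert is one, and it is mandatory.
- That the per-cohort criterion alone gives the size. Comparing 8 with 6 participants per cohort yields 45%, 43%, 39% and 31% of holds cleared at 2%, 5%, 10% and 20%, but this ignores the study-wide halt.

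The sentinel case is also better protected than the 50% suggests, since the SMC must look before others are dosed. What the reply does not supply is a criterion for method-caused events. Each safeguard ends either in judgement or in the IMP-related criteria, and the one written example steers that judgement towards resuming.

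**Conclusion.** The point holds as a gap in the predefined rule, of modest weight. Section 6.7.1 allows a hold to be cleared on placebo status in cohorts where placebo participants undergo the method being tested, and no numeric halt rule covers events caused by that method. The same wording applies to syringe-driver placebo in Cohorts 1 and 3, but matters less there because that method is established in the programme.

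The finding rests on the wording. The 40%, 32%, 22% and 9% only illustrate its size: the risks are assumed, event order is ignored, and every placebo event is treated as cleared although clearing is optional. Counting clinically significant AEs under the study-wide rule would lower them. In absolute terms, a clearable hold arises in roughly 0.4% to 4.4% of manual-push cohorts over the risks shown.

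**What to change.** Add one sentence after the placebo example in Section 6.7.1: placebo status alone does not clear a hold for an injection-site, infusion or other administration-related event, and the SMC reviews that event before dosing by that method resumes. Dosing by the other method need not wait.

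This needs no new data, staff or visits. A change to the stopping-rule text probably requires a substantial amendment; the same sentence in the SMC Charter would give most of the benefit, probably without one. The downside is that a chance event on placebo may briefly pause dosing by that method until the SMC has met.
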